Not applicable.

7. Plan for reporting unanticipated problems or study deviations.

The plan below is specifically for the **Intervention Arm**.

The PI ([name]) and co-I ([name]) will bear the responsibility for data and safety monitoring. An independent data safety monitor ([name], Assistant Professor, General Internal Medicine) will be employed as well as below.

During data collection points at 6 and 12 months, adult participants would be queried about possible adverse events (AEs), specifically interim ED visits or hospitalizations, for both themselves and the child enrolled in the study. (see uploaded Adverse Events form). Any and all adverse events would be reviewed by the PI, [name] as co-I and also the independent safety monitor for review; adverse events will be reported to the Johns Hopkins School of Medicine IRB, as well as NIH project office according to the prevailing policies of these review bodies. Study team members will receive training regarding adverse event documentation and reporting.

In addition, adult weight changes and child BMI changes will also be reviewed as follows: at 6 and 12 months, a research team member will send to the independent study monitor a report with participant study ID, age and % weight change for adults or change in BMI for children over the past 6 months. Significant changes in adult weight or child weight-for-height over the review period will prompt the independent safety monitor to notify [name] or [name] to refer the participants to their primary care physician for additional evaluation.

Of note, the Brancati Center DPP clinical program has team members who provide medical oversight of all participants in the DPP, and adult participants in the study will also be under this as per routine care. During weekly team meetings as part of routine care, adult participants weight changes are reviewed for all participants.

8. Payment and Remuneration

Intervention Arm

Specific to study procedures, the adult participant (as the representative of the adult-child dyad) will be remunerated via \$50 gift cards with completion of data collection at each time point (baseline, 6 month, 12 month), for a maximum of \$150 related to study procedures. In addition, the Brancati Center's DPP provides program-related supports that will continue to be the same for all participants.

Concurrent Control Group (Control Arm)

Specific to study procedures, the adult participant will be remunerated with a \$30 gift card with completion of the single data collection point.

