1) Recruitment from adults who are outreached for the Brancati Center's Diabetes Prevention Program. After these adults are deemed eligible for the Diabetes Prevention Program for screening, they would be asked the following question by Brancati Center DPP team members "There is a research study for DPP participants that you may be eligible for. This study involves adults in the DPP and children ages 5 through 12 years that they care for. As part of the study, you would be enrolled in a "family-oriented" version of the DPP, which would include some sessions related to children's healthy behaviors in the second half of the program. In addition to you participating in the DPP, you and one child would be asked to complete surveys and provide some other data 3 times during the program, and potentially participate in an interview after the program. You would be compensated \$50 for each of the data collection points. Would you be interested in learning more about the study?" If potential participants are interested, their contact information would then be provided to the Family DPP study team for recruitment and screening eligibility.

2) Flyers in clinical sites and community partner sites, with the flyer also posted to the Brancati Center's Facebook Page and website. We will also request community partner organizations in Baltimore to disseminate the flyers to their community members (such as through in-person events, via e-mail or with announcements, or by posting on their social media sites). We will also advertise via paid Facebook advertisements. We will also request community partner organizations in Baltimore to share with their community members including at in-person events and via e-mail or by posting on their social media sites. We will also advertise via paid Facebook advertisements. The flyers will have a contact study email and also phone number for participants to call. The phone number will be that of a study team member; the email will only be accessible to study team members. A telephone screening script will be used when a study team member discusses the study with potentially interested participants, to assess eligibility. If a participant provides their email address as contact information, we will outreach via telephone and also if needed via email from the [contact] email account.

The email outreach will read:

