"Thank you for your interest in the Family Diabetes Prevention Program Pilot Study. (We have tried to reach you also via the telephone number you provided [note: this will be included if applicable]).

You may also reach us via calling [contact] or [contact]), or responding to this email with the phone number you would like us to call and/or if there are specific days or times you would like us to call you.

Thank you again for your interest.

Sincerely,

[name] [name]
Principal Investigator

Family Diabetes Prevention Program Pilot Study

3) Recruitment from clinical providers (NPs, PAs or physicians) at sites such as East Baltimore Medical Center (if approved by JHCP Research committee). The study team will present to providers at this site to describe the study and general eligibility criteria; providers will be provided flyers. Providers will be asked only to provide the patient's name and contact information via a secure email to the study team. They will be asked to document in the chart "I discussed the referral of the patient to the Family Diabetes Prevention Program team for the Family DPP pilot study. The patient agreed to the referral."

4) Recruitment via the Johns Hopkins ICTR's Johns Hopkins Studies Facebook Page, which includes Facebook advertising via the ICTR to recruit study participants for Johns Hopkins Studies; the Facebook Ad Plan is uploaded as a document in question 13.

Screening eligibility for Intervention Arm

Potential adult participants who are referred by the Brancati Center DPP team as per their interest in learning more about the study, will have already undergone screening to ensure they meet DPP-related inclusion criteria (are eligible as adults for participation in the DPP), as per routine protocols for the DPP. Screening of these adults for additional inclusion criteria for the study (e.g., being a caregiver of an eligible child), will be conducted by a study team member via a separate outreach call. For those potential adult participants recruited via other means, the study team member will also conduct DPP eligibility screening as per the Brancati Center's practices.

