For child participants, screening eligibility will be conducted via the adult participant. It is possible, given the definition of caregiver that is used, that the caregiver may not be able to answer specific questions regarding the child's inclusion criteria. If this is the case, the child's parent or legal guardian will be contacted to confirm the child's eligibility.

If a caregiver has more than 1 child in the eligible age range, the study team member conducting the screener will use a random number generator to select one child randomly, and assess the eligibility of this child. If the child is not eligible, then the next child's eligibility will be assessed. If the caregiver expresses a strong desire to assess the eligibility of a certain child in particular, then the study team member will be advised to start with the eligibility screening of this child.

Enrollment of the Intervention Arm

- Enrollment of adult participants (and child participants) in the intervention arm, after eligibility screening, completion of adult consent process and the child assent (with parent or legal guardian consent) process (Details regarding consent and assent as detailed in Sections 14-17 of the eIRB application).
- Any related enrollment processes related to the adult participant's participation in the DPP as routine care, will be conducted by the Brancati Center team as per routine practices for DPP enrollment.
- For the child, the enrollment form will confirm parent/legal guardian contact information (emergency contact information), the child's pediatrician, and food or other allergies to be aware of.

Randomization

- Participants will not be randomized to the intervention. All participants who are recruited for the intervention arm will be engaged in the FDPP intervention.

Recruitment and Screening Eligibility: Concurrent Control Group (Control Arm)

Recruitment of Concurrent Control Group (Control Arm):

The concurrent control group will consist of adults in the Brancati Center's DPP (who started the program within 6 months of the Intervention group) and who have children less than 18 years of age living in their household. We will recruit adult participants for the concurrent control groups through several means as detailed in "Section 13." This will include

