The DPP (and FDPP) interventions are designed for prevention of type 2 diabetes in adults with prediabetes. Some adult participants may progress to type 2 diabetes while participating in the FDPP; the CDC's guidelines are that these individuals can remain in the DPP lifestyle intervention (given the benefits of lifestyle modification). The Brancati Center team confers with the participant's primary care provider if this were to occur (development of type 2 diabetes) to confirm that the participant is recommended to continue in the DPP.

h. Description of what happens to participants receiving therapy when study ends or if a participant's participation in the study ends prematurely.

Participants will be instructed to continue with routine medical care when the program ends or if their participation ends prematurely.

i. If biological materials are involved, please describe all the experimental procedures and analyses in which they will be used.

Not applicable.

4. Inclusion/Exclusion Criteria

Intervention Arm

The study will enroll adult-child dyads in the Intervention Arm.

Adult inclusion criteria will include meeting all of the following:

- 1) CDC national criteria for enrollment in the DPP (as used by the Johns Hopkins Brancati Center's DPP programs):
 - Be 18 years of age or older and not pregnant at time of enrollment
 - Have a body mass index (BMI) of $\geq 25 \text{ kg/m}^2$ ($\geq 23 \text{ kg/m}^2$, if Asian American).
 - Meet either one of the criteria
 1. Have a recent (within the past year) blood test meeting one of these specifications:
 - i. Fasting glucose of 100 to 125 mg/dl (CMS eligibility requirement for Medicare DPP suppliers is 110 to 125 mg/dl)
 - ii. Plasma glucose measured 2 hours after a 75 gm glucose load of 140 to 199 mg/dl
 - iii. A1c of 5.7 to 6.4%.
 2. Clinically diagnosed gestational diabetes mellitus (GDM) during a previous pregnancy
 3. A positive screening for prediabetes based on the CDC or American Diabetes Association Diabetes Screening Test (a brief questionnaire)
- 2) being a primary caregiver of at least one eligible child aged 5 through 12 years at time of recruitment (defined as caring for the child, with a responsibility for the child's food, sleep and activity habits, at least 3 days out of the week)

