Exclusion criteria for adults will reflect CDC national DPP exclusion criteria. Specifically, adults will be excluded if they are: 1) pregnant; 2) have end-stage renal disease; 3) have type 1 or type 2 diabetes. They will also be excluded if they are concurrently enrolled in a structured weight management program.

Children for whom the eligible adult is a primary caregiver (parent or guardian who cares for the child 3 or more days out of the week), will be considered eligible participants if 1) they are aged 5 through 12 years at time of recruitment; 2) they do not have a medical condition which leads to inability to comply with general pediatric dietary or physical activity goals; and 3) they are not concurrently enrolled in a structured weight management program.

Concurrent Control Group

Inclusion criteria for adults in the control group will include meeting all of the following:

- 1) Participant in the Brancati Center's Diabetes Prevention Program, in a group that has started within 6 months of Intervention Arm group start
- 2) Lives with a child less than 18 years of age in their household

5. Drugs/ Substances/ Devices – Not applicable

6. Study Statistics

a. Primary outcome variable.

Primary outcomes will examine process measures.

These will include:

- I. Feasibility measures (measuring recruitment, retention and measurement of outcomes, cost):
 - a. Recruitment rate, measured as % of eligible caregivers consented to study/time
 - b. Caregiver attendance, defined as % of adult, child-focused and all sessions attended
 - c. Child attendance, defined as % of sessions requiring child participation attended
 - d. Survey administration, defined as mean time for administration of surveys
 - e. Total cost per group of program delivery
- II. Acceptability measures
 - a. Including mean scores on Likert scale-based questions re: satisfaction with program content & structure, willingness to recommend to others
- III. Fidelity, as measured by a fidelity checklist that will be completed by a study team member observing the child-focused sessions (specifically, the child-focused sessions delivered to adult participants), and will include measures:
 - a. % of tasks/content delivery per session from coach checklist
 - b. Total & average scores per domain from observer checklist

b. Secondary outcome variables.

Secondary outcome variables will preliminarily examine:

1. Proximal intervention targets

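### In the DPP-outreach recruitment route, caregivers who decline the first interest question cannot enter the denominator of the primary recruitment rate, so the figure is consent among interested, screened-eligible adults

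*Combined protocol and SAP*

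**What the plan says.** The measure is given in Section 6.a, item I.a: "Recruitment rate, measured as % of eligible caregivers consented to study/time". The protocol does not say operationally who counts as eligible. The data-collection part of Section 3.a has study team members track it, and Section 6.c analyses it descriptively.

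Section 3.a (Recruitment for Intervention Arm, item 1) describes the DPP-outreach route. Once adults have been found eligible for the DPP, "they would be asked the following question by Brancati Center DPP team members". The script describes the study, mentions children aged 5 through 12, and ends by asking whether the adult would like to hear more. Then: "If potential participants are interested, their contact information would then be provided to the Family DPP study team for recruitment and screening eligibility".

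Section 3.a (Screening eligibility for Intervention Arm) says what is known at that moment. Referred adults "will have already undergone screening to ensure they meet DPP-related inclusion criteria". Caregiver status comes later: "Screening of these adults for additional inclusion criteria for the study (e.g., being a caregiver of an eligible child), will be conducted" in a further contact, which "will be conducted by a study team member via a separate outreach call". On the child's side, "For child participants, screening eligibility will be conducted via the adult participant".

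Section 4 makes caregiver status an inclusion criterion: "being a primary caregiver of at least one eligible child aged 5 through 12 years at time of recruitment".

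**The concern.** An adult can be called an eligible caregiver only after the study team has asked about the child. In route 1 that happens only for adults who have already said yes to the DPP team. A caregiver of a seven-year-old who says no is, in the records described, indistinguishable from an adult with no child in range who says no. Neither reaches the study team, and no section describes a log of these refusals.

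The route-1 percentage therefore describes how many adults consent once they are interested and found eligible. That is a legitimate quantity, but it does not tell a planner how many enrolments to expect from a given number of eligible caregivers in a DPP intake. Feasibility is the primary objective, and a reader could easily take this figure as uptake. If refusals are not recorded when they occur, the missing count cannot be rebuilt afterwards.

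The point is about who is in the denominator. It is separate from the division by time in the same definition.

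**Working it through.** The documents state no expected recruitment rate, interest rate, sample size or threshold, so there is no planned figure to reproduce. The check is the order of events, followed by simple proportions.

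**Order of events in route 1** (Sections 3.a and 4)

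1. DPP eligibility is established by the DPP team.
2. The DPP team asks about interest.
3. Only interested adults are referred.
4. The study team screens caregiver and child criteria in a separate call.
5. Consent is sought.

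The status needed for the denominator is first obtained at step 4. Refusals at step 2 are lost to it. Refusals after step 4 are kept.

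**Inputs, all assumed**

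- i: share of eligible caregivers asked who express interest at step 2
- k: share consenting among those interested and screened eligible (80% for illustration)
- w: share of all eligible caregivers asked who come through route 1

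The formulas take every interested eligible adult to be reached and screened.

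**Route 1 alone**

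- Percentage on the screened-eligible denominator = k
- Percentage on all eligible caregivers asked = i × k
- Ratio = k / (i × k) = 1/i, which does not depend on k

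| i | screened-eligible (k) | all eligible asked (i × k) | ratio 1/i |
|---|---|---|---|
| 0.3 | 80% | 24% | 3.33 |
| 0.5 | 80% | 40% | 2.00 |
| 0.7 | 80% | 56% | 1.43 |
| 0.9 | 80% | 72% | 1.11 |

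The two agree only at i = 1.

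**All routes pooled.** Take the other routes as having no refusal step before screening, and the same k. The ratio is then 1 / (w × i + 1 − w). For example, with w = 0.5 and i = 0.3: 0.5 × 0.3 + 0.5 = 0.65, and 1/0.65 = 1.54.

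| w | i = 0.3 | i = 0.5 | i = 0.7 |
|---|---|---|---|
| 0.25 | 1.21 | 1.14 | 1.08 |
| 0.50 | 1.54 | 1.33 | 1.18 |
| 0.75 | 2.11 | 1.60 | 1.29 |

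**The other possible denominator.** If the team divided by every DPP-eligible adult asked, of whom a share c are eligible caregivers, the result would be c × i × k. With c = 0.2 to 0.4 (assumed), i = 0.5 and k = 80%, that is 8% to 16%, against 40% among eligible caregivers. This errs the other way and is not a percentage of eligible caregivers.

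**The case against.** The strongest reply is that the plan never says it will divide by screened-eligible adults only. A reader might infer that the protocol prescribes an inflated percentage. It does not: the denominator is undefined, and the upward direction follows from the described workflow, not from a stated rule. What stands is that neither count available from that workflow gives the stated measure. One omits eligible decliners and the other includes non-caregivers.

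A reader might also infer that all eligible caregivers who decline are lost. Only those who decline the first question are; those who decline after screening are counted.

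Nor do the documents support a headline size such as threefold for the primary outcome. No interest rate is given, the first question asks only about hearing more, so interest may be high, and pooling four routes dilutes the effect.

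The documents do not say that a later trial will be sized from this figure. Section 3.f mentions informing a larger trial, but in connection with the control group and adult outcomes. Consent among screened-eligible adults is a coherent feasibility measure if it is labelled as that.

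Unseen material matters too. Recruitment detail is referred to Section 13 of the IRB application, and the DPP has its own screening processes under another IRB protocol. A contact log may exist there, so its absence cannot be established; it can only be said that none is described here.

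Finally, the measure is descriptive, with no threshold or test, so no error rate is affected. This limits the consequence to interpretation and planning. For flyers and Facebook, self-selection is inherent in the method and there is no countable group that was asked.

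**Conclusion.** The point holds for recruitment route 1. As described, caregivers who decline the first interest question cannot be identified as eligible, and the percentage obtainable is consent among interested, screened-eligible adults. It exceeds uptake among all eligible caregivers asked whenever any of them declines at that question.

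The factor is 1/i: 3.3 to 1.1 for an assumed i of 0.3 to 0.9 in route 1. It is smaller when pooled, for example 1.54 to 1.18 for i of 0.3 to 0.7 if half of the eligible caregivers asked come by this route. The direction follows from the order of events, provided no unseen log captures caregiver status among decliners. The size cannot be fixed from the documents. The change is worth making because this is the first-listed primary feasibility measure and unlogged refusals are not recoverable.

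**What to change.** **At the existing route-1 contact.** Have the DPP team ask every DPP-eligible adult one yes/no question: do they care for a child aged 5 through 12 at least 3 days a week? Log the answer together with interested or not interested.

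**In Section 6.a, I.a.** Report route 1 as counts at each stage: asked, potentially eligible caregiver, interested, screened, eligible, consented. Give two labelled percentages:

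- consented among screened-eligible adults;
- consented among potentially eligible caregivers asked.

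State that the second is a lower bound on uptake. A yes to one question is not full eligibility: the child's medical condition and enrolment of adult or child in a structured weight management program are not checked in decliners. The denominator therefore includes some ineligible adults while the numerator is unchanged. This assumes that eligible caregivers answer the question correctly.

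**Other routes.** Report flyers, provider referral and Facebook separately, as consent among screened-eligible volunteers.

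**Contacts already made.** Section 6.c indicates that recruitment has begun. State the date from which the tally was kept, and use any existing DPP contact log for earlier contacts.

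**Cost.** One question and a tally on a contact already being made, a wording change in Section 6.a, and a less favourable recruitment figure.

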 - Physical Activity (discussing physical activity guidelines and how to support kids to be active on a daily basis)
 - Screen time (discussing screen time guidelines, smart screen time use and strategies to help limit children’s screen time)
 - Family Exercise Activity (a session in which adults and children will be guided through a fun physical activity, such as Zumba).
 - Family Cooking Activity (a session in which adults and children will be guided through preparing a healthy meal.)
 - A sample Family DPP schedule included in this IRB application under “Supplementary Material.”

- 3) **Note on children as participants in the FDPP:** Both the FDPP and National DPP interventions are intended to be delivered primarily to the adult participant (caregiver of the child). For the FDPP, children may be present during child-focused modules as noted above. During these sessions, the children will engage in age-appropriate activities, games and discussions to learn basic concepts about healthy lifestyle behaviors. This would be done separate from the adult caregivers (a separate room or Zoom room, if possible), and then they will join the adult caregivers at the end of the session for a group discussion.
- 4) Concurrent Control Group: The adults in the concurrent control group will be recruited (as detailed below) from participants in the Brancati Center's Diabetes Prevention Program.

Recruitment, Screening Eligibility and Enrollment: Intervention Arm

Recruitment for Intervention Arm:

We will recruit adult participants, and one index child, through several means as detailed in "Section 13". This will include

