c. Study duration and number of study visits required of research participants.

For Intervention Arm:

Study participants would be engaged for approximately 12-14 months. This time period would involve the delivery of the family-oriented DPP (or control group would receive DPP) lifestyle intervention, during which we would have 3 study-specific visits (at baseline, 6 months and 12 month data points).

For Concurrent Control Group (Control Arm):

Study participants would be engaged for one telephone-based survey administration call.

d. Blinding, including justification for blinding or not blinding the trial, if applicable.

We will not be blinding participants in this pilot study. It would not be feasible to blind participants in the 2 different arms/groups, as they are receiving different interventions (Family DPP versus being enrolled in the DPP).

e. Justification of why participants will not receive routine care or will have current therapy stopped.

Not applicable; the DPP itself is deemed routine care for adults with prediabetes, and enrollment in DPP does not interfere with receipt of other routine medical care. The family-oriented version of the DPP (FDPP) will consist of all elements of the DPP, with additional augmentations with respect to family or child-oriented content, as described earlier, and similarly will not interfere with receipt of other routine medical care for adults or children.

f. Justification for inclusion of a placebo or non-treatment group.

We have revised our study protocol from the original version (dated 4/20/22), to enroll all eligible study participants in the intervention arm. But we will plan on enrolling adult DPP participants with children under the age of 18 in a concurrent control group. This concurrent control group would consist of adult participants of the Brancati Center’s DPP program

who are living in a household with children. In this control group, we would examine adults' attendance and DPP outcomes related to weight loss and physical activity group. This would enable us to preliminarily explore differential impact of the FDPP versus DPP on adult health outcomes, informing elements of a larger comparative effectiveness trial comparing the FDPP versus the DPP.

g. Definition of treatment failure or participant removal criteria.

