 - a. Caregiver (adult participant) knowledge and attitudes towards healthy-related behaviors
 - b. Perceived self-efficacy for behavioral change
 - c. Parenting self-efficacy for behavioral change
 - d. Family Home Environment
2. Caregiver (adult participant) Health behaviors and health outcomes
 - a. Physical activity- total minutes of moderate/vigorous physical activity in weeks preceding and whether caregiver meets DPP physical activity goal of 150 minutes/week of moderate-vigorous physical activity; and dietary
 - b. Dietary patterns

- c. Percent weight loss from baseline
- 3. Child health behavior and health outcomes
 - a. Physical activity- minutes/day
 - b. Screen time (hours/day)
 - c. Fruit and vegetable intake
 - d. Sugary beverage intake
 - e. Sleep duration and sleep behaviors
 - f. BMI z-score change
- c. Statistical plan including sample size justification and interim data analysis.

As the main objective of this study is evaluating FDPP feasibility and acceptability measures, sample size is primarily informed by budgetary constraints and our experience recruiting individuals for the DPP as well as recruitment for the study thus far.

Feasibility, acceptability and fidelity measures will be analyzed with descriptive statistics (Table 2). Intervention targets will be analyzed as continuous variables (means or numerical scores). Caregiver and child health behaviors will be analyzed as continuous variables (average value/day) and a binary variable (achievement of goal). The caregiver health outcome will be modeled as a continuous variable (percent of weight loss from baseline) and binary variable (achievement of 5% weight loss goal). The child health outcome is the BMI Z-score, a continuous variable. Within-groups, we will use 1) paired-t tests to analyze pre-post changes (from baseline to 6 months and baseline to 12 months) of continuous variables; and 2) McNemar's exact test to examine pre-post changes in proportion achieving behavioral and outcome goals (binary variables). Between groups, we will use 1) 2-sample t-tests to compare the magnitude of mean group change in values of continuous variables; and 2) Fisher's exact test to compare proportion achieving goals at 6 and 12 months. If continuous variables do not meet distribution assumptions necessary for use of parametric tests (t-tests), we will use appropriate non-parametric tests (Mann-Whitney test or, for paired data, Wilcoxon signed-rank test).

- d. Early stopping rules.

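### Intervention adults can be recruited from outside DPP intake while controls cannot, so the exploratory FDPP-versus-DPP contrast may partly reflect recruitment source, which Section 6.c does not examine

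*Combined protocol and SAP*

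**What the plan says.** Allocation is by recruitment stream: "Participants will not be randomized to the intervention" (Section 3.a, Randomization).

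Section 3.a, Recruitment for Intervention Arm, lists four routes:

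- Route 1: "Recruitment from adults who are outreached for the Brancati Center's Diabetes Prevention Program". These adults have already been found eligible for the DPP when the study is mentioned to them.
- Route 2: "Flyers in clinical sites and community partner sites, with the flyer also posted to the Brancati Center's Facebook Page and website", together with community partner organizations and paid Facebook advertisements.
- Route 3: referral by clinical providers directly to the study team, conditional on a committee's approval.
- Route 4: an institution-wide studies page, "which includes Facebook advertising via the ICTR to recruit study participants for Johns Hopkins Studies".

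The screening text separates route 1 from the rest: "For those potential adult participants recruited via other means, the study team member will also conduct DPP eligibility screening".

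For the comparison group, "The adults in the concurrent control group will be recruited (as detailed below) from participants in the Brancati Center's Diabetes Prevention Program". Both listed control routes reach adults attending a DPP group or assigned to one that has not started, and Section 4 makes DPP participation an inclusion criterion.

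Section 3.f says the control group is there to "preliminarily explore differential impact of the FDPP versus DPP on adult health outcomes" and so inform a larger comparative effectiveness trial. Section 6.c compares the groups by "2-sample t-tests to compare the magnitude of mean group change in values of continuous variables", by Fisher's exact test for goals, or by a non-parametric equivalent. It has no adjustment, matching, stratification or sensitivity analysis by recruitment source.

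**The concern.** People who answer a study flyer or advertisement, or whom a provider sends to the study, may differ from people who came through DPP outreach in ways that affect weight loss, activity and attendance. If so, a difference between the arms can appear when the family content does nothing, or a real effect can be masked. The unadjusted comparison cannot tell these apart, and the plan does not say that route will be kept as a variable.

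The stake is limited but real. The contrast is secondary and exploratory, yet Section 3.f gives it a planning role for the larger trial. An unexamined source effect would pass into that planning as if it were a program effect.

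**Working it through.** The documents state no N, SD, power or route mix for this contrast, so there is no figure to reproduce. The check sets the two recruitment descriptions side by side and then reads Section 6.c.

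**Routes by arm**

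| Arm | Through DPP intake | Outside DPP intake |
|---|---|---|
| Intervention (4 routes) | 1 (DPP outreach) | 3 (flyers and paid advertisements; provider referral; studies Facebook page) |
| Control (2 routes) | 2 (current group members; adults assigned to a group) | 0 |

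**Which analyses are exposed**

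- Percent weight loss, the 5% goal and physical activity are adult outcomes available in both arms from routine DPP data. Section 6.c gives them between-group tests.
- Attendance is to be compared between groups according to the Abstract, but Section 6.a lists it as a feasibility measure and Section 6.c analyses those descriptively. No test of attendance is specified.
- Feasibility, acceptability and fidelity as primary outcomes describe the FDPP and do not rest on the contrast.

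**Illustration of size (all inputs assumed)**

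Let p be the share of FDPP adults from routes 2-4. Let d be the difference in a continuous outcome such as percent weight loss, in SD units, between those adults and DPP-intake adults under the same program. With no program effect:

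bias in the mean difference = p × d

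- Smallest case: 0.25 × 0.2 = 0.05 SD
- Middle case: 0.5 × 0.5 = 0.25 SD
- Largest case: 0.75 × 0.5 = 0.375 SD

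With n per arm, the standard error is √(2/n) SD. By the normal approximation, the rejection rate of a nominal two-sided 5% test is 1 − Φ(1.96 − bias/SE) + Φ(−1.96 − bias/SE).

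| Bias | n = 15 per arm | n = 30 per arm | n = 60 per arm |
|---|---|---|---|
| 0.05 SD | 5.2% | 5.4% | 5.9% |
| 0.25 SD | 10.5% | 16.2% | 27.8% |
| 0.375 SD | 17.7% | 30.6% | 53.7% |

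The effect runs from negligible to serious, depending on quantities that the documents do not give. The table shows sensitivity and does not estimate the bias in this trial.

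**What the route-1 comparison costs in precision**

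With equal arms and equal SDs, keeping only the share 1 − p of FDPP adults multiplies the standard error by √{[1/(1 − p) + 1]/2}:

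- p = 0.25: √[(1.333 + 1)/2] = 1.08
- p = 0.5: √[(2 + 1)/2] = 1.22
- p = 0.75: √[(4 + 1)/2] = 1.58

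The interval would be about 8% to 58% wider over this range.

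**The case against.** The strongest case against has four parts.

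- **The streams may overlap.** The documents do not say how DPP enrollees first reached the program. Route 2 uses the center's own web and Facebook pages and community partner sites, where DPP sessions may also be held. Route 3 may never open. Both recruitment lists also point to a Section 13 that is not in the text. This stands: a reader might infer from three outside routes against none that the arms come from distinct populations, and the documents do not establish that.
- **Route 1 is not a clean match to controls.** Route-1 adults hear the same family-study offer, with $50 per data collection point, and accept it. They must be primary caregivers of a child aged 5 through 12, whereas controls need only live with a child under 18. Some controls join after their group has started, so they may be selected for staying. This also stands. A reader might infer that the route-1 estimate is the unbiased one, but it removes only the source difference.
- **The baseline data might capture the relevant differences.** A reader might infer that the control survey misses traits such as motivation or digital access. The survey instruments are not in the supplied text, so that cannot be asserted. Whatever is collected, Section 6.c does not use it to adjust the contrast.
- **This is an openly non-randomized pilot.** That limits how much the point matters. It does not answer it, because Section 6.c still specifies between-group tests and Section 3.f gives the result a use. Common DPP eligibility practices limit clinical differences between the arms, but not differences in why or how people joined.

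**Conclusion.** The point holds as a limitation of the exploratory adult contrast that can be examined cheaply. Three of four intervention routes lie outside DPP intake, neither control route does, and Section 6.c pools all routes without adjustment. Differences in adult percent weight loss, the 5% goal and activity, and in described attendance, may therefore partly reflect recruitment source.

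Size and direction are unknown. The range of 0.05 to 0.375 SD rests on assumed shares of 25-75% and assumed differences of 0.2-0.5 SD. If the streams overlap heavily, the bias could be close to zero.

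A reader might go further and conclude that the contrast is biased in a known direction, or that the main findings of the pilot are compromised. The documents support neither. The difference in routes shows that confounding is possible but does not measure it, and the primary process outcomes do not depend on it.

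**What to change.** 1. Keep recruitment route as an analysis variable. Screening already distinguishes adults referred by the DPP team from those recruited by other means, so this needs no new contact with participants.
2. Within the FDPP arm, tabulate baseline characteristics, attendance and percent weight loss by route (route 1 versus routes 2-4). Everyone in that arm gets the same program, so the table gives direct, if imprecise, evidence on whether source matters.
3. Add to Section 6.c a prespecified sensitivity comparison of route-1 intervention adults with controls for each adult between-group outcome. Report it as an estimate with a 95% confidence interval beside the all-route result.
4. Interpret the contrast for the larger trial in light of both estimates, with neither decisive. State that the route-1 comparison leaves in place the acceptance of a paid family study, the different child criteria and the recruitment of some controls after their group has started.

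Recruitment, eligibility and program delivery do not change, and all routes stay in the feasibility and acceptability analyses. The cost is analysis-plan wording, one table and one subset comparison with a smaller FDPP sample and a wider interval. If few adults come through route 1, that comparison will say little and should be reported as such.
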